12.4. Primary Endpoint

All safety endpoints will be summarized using the SP.

The MedDRA will be used to code all AEs to a system organ class (SOC) and a preferred term.

The patient incidence of all TEAE, SAEs, related AEs, AEs leading to withdrawal of IMP, fatal AEs, and AESI will be tabulated by system organ class and preferred term in descending order of frequency. If appropriate, exposure-adjusted patient incidence rate will also be provided.

Adverse events occurred in the parent study and continued into the OLE study without change in severity will be captured in the parent study only.

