11. ADVERSE AND SERIOUS ADVERSE EVENTS

11.1. Adverse Events

11.1.1. Definition of Adverse Events

An AE is defined as any untoward medical occurrence in a clinical investigation patient administered a pharmaceutical product, including control, and which does not necessarily have a causal relationship with treatment. The investigator is responsible for ensuring that any adverse events observed by the investigator or reported by the patient are recorded in the patient's medical record.

An AE can be:

- Any unfavorable and unintended sign/symptom, including an abnormal laboratory finding, or disease temporally associated with the use of a medicinal product, whether or not considered related to the medicinal product
- Any new disease or exacerbation of an existing disease
- Laboratory abnormality or diagnostic test abnormalities (eg, electrocardiogram [ECG] or X-ray) should be reported as an AE if one of the following occurs
 - Treatment required due to the abnormality
 - Discontinuation of IMP
 - Per Investigator judgement

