11.1.3. Reporting for Adverse Events

All AEs occurring during the course of the study (starting from signing informed consent through 30 days after last dose of bempedoic acid) will be collected on the AE eCRF. Patients should be instructed to report any AE that they experience to the investigator. Investigators should make an assessment for AEs at each visit and record the event on the appropriate AE eCRF.

Wherever possible, a specific disease or syndrome rather than individual associated signs and symptoms should be identified by the investigator and recorded on the eCRF. A cluster of signs and symptoms that results from a single cause should be reported as a single AE (eg, fever,

Bempedoic Acid Clinical Study Protocol 1002-050

elevated white blood cells [WBC], cough, abnormal chest X-ray, etc, can all be reported as "pneumonia" if that is the final diagnosis). However, if an observed or reported sign or symptom is not considered a component of a specific disease or syndrome by the investigator, it should be recorded as a separate AE on the eCRF. Additionally, the condition that led to a medical or surgical procedure should be recorded as the AE, not the procedure itself.

Any medical condition already present at screening or baseline should not be reported as an AE unless the medical condition or signs or symptoms present at baseline worsens in severity or seriousness at any time during the study. In this case, it should be reported as an AE.

Clinically significant abnormal laboratory or other examination findings that are detected during the study or are present at baseline and significantly worsen during the study should be reported as AEs. The investigator will exercise his or her medical and scientific judgment in deciding whether an abnormal laboratory finding or other abnormal assessment is clinically significant. Significant abnormal laboratory values occurring during the clinical study will be followed until repeat tests return to normal, stabilize, or are no longer clinically significant. Any abnormal test that is determined to be an error does not require reporting as an AE.

Each AE is to be evaluated for duration, severity, seriousness, and causal relationship to the IMP. For each AE, the following information will be recorded:

- Description of the event (eg, headache)
- Date of onset
- Date of resolution (or that the event is continuing)
- Action taken as a result of the event
- Seriousness of the event
- Severity of the event

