#### 3.2.1 Adverse Events

The evaluation of adverse events (AEs) will include only incidence of TEAEs, defined as AEs that begin or worsen on or after the date of first dose of study drug administration in open-label extension (OLE) period and until 30 days after last dose of study drug. AESI will be examined further (See Section 5.4.2 for more information).

Clinical endpoints (details see section 4.2) will be collected and adjudicated by an independent Clinical Events Committee (CEC). Clinical endpoints will also be reported as AEs.

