#### 5.4.1 Adverse Events (AEs)

AEs will be coded using the Medical Dictionary for Regulatory Activities (MedDRA) Version 20.1 or later and will be categorized by system organ class (SOC) and preferred

Confidential

Page 15 of 27

Page 117 of 129

term (PT). Summary tables will focus on TEAEs; however, listings will include all AEs (with non-TEAEs flagged). An additional AE listing will be provided for AEs occurred during rollover period.

In summary tables, TEAEs will be counted as "Not Related" if relationship to study drug was recorded as 'Not Related' or "Unlikely". Events will be counted as "Related" if relationship to study drug was recorded as 'Possible', 'Probable', 'Definite' or if relationship to study drug is missing.

The severity of the AE will be characterized as mild, moderate, or severe, to the following definitions:

- Mild: Events are usually transient and do not interfere with the patient's daily activities
- Moderate: Events introduce a low level of inconvenience or concern to the patient and may interfere with daily activities
- Severe: Events interrupt the patient's usual daily activity, are incapacitating with inability to do usual activities, or significantly affect clinical status and warrant intervention and/or close follow-up

Overviews of TEAEs will include total number of TEAEs, and patient incidence of TEAEs, TESAEs, treatment-related TEAEs, treatment-related TESAEs, IMP withdrawal due to TEAEs, TEAEs with fatal outcome. Individual TEAE summary will be presented by previous treatment group in parent study and overall containing the following counts and percentages for:

- patients with TEAEs by SOC and PT
- patients with TEAEs by PT
- patients with TEAEs by SOC, PT, and maximum severity
- patients with treatment-related TEAEs
- patients with treatment-related TEAEs by PT
- patients with treatment-related TEAEs by SOC and PT
- patients with treatment-emergent serious adverse events (TESAEs) by SOC and PT
- patients with TESAEs by PT
- patients with TESAEs by SOC, PT, and maximum severity
- patients with treatment-related TESAEs
- patients with treatment-related TESAEs by SOC and PT
- TEAEs leading to withdrawal of IMP by SOC and PT
- fatal TEAEs by SOC and PT

Preferred terms for TEAEs that occurred in more than 1% of subjects overall will be plotted using the overall group. This plot will be repeated for TESAEs in the overall group.

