#### Confidential

Page 16 of 27

In addition, summary tables will be provided, by prior treatment group and overall, for the number and percent of patients experiencing:

- adjudicated major adverse cardiovascular events and mortality (MACE) by event type
- non-CV deaths (non-MACE),
- nonfatal myocardial infarction [MI] (MACE),
- nonfatal stroke (MACE),
- hospitalization for unstable angina (MACE),
- coronary revascularization (MACE),
- noncoronary arterial revascularization (non-MACE),
- hospitalization for heart failure (non-MACE) using standardized definitions.

The TEAE, treatment-related TEAE, TESAE, and AESI summaries by SOC, PT and maximum severity will be provided for relevant subgroups described in 5.2.5 with the exception of baseline LDL category.

The AE overview summaries will count a patient at most once in each AE category (at the "highest/most extreme" designation of each category regardless of preferred term) and percentages will be based on the total number of patients in the safety population.

In addition to a comprehensive listing of all AEs (with non-TEAEs flagged), separate listings will be generated for serious adverse events, TEAEs resulting in withdrawal of study drug, and TEAEs with a fatal outcome, investigator reported major adverse cardiovascular events and mortality, and adjudicated major adverse cardiovascular events and mortality.

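### A parent-study adverse event that continues at unchanged severity and makes a patient stop drug in the OLE is left out of the adverse-event withdrawal tables and listing and shows only as a disposition reason

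*Protocol*

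**What the plan says.** Protocol section 12.4 sets the carry-over rule: "Adverse events occurred in the parent study and continued into the OLE study without change in severity will be captured in the parent study only". The recording rule for sites in section 11.1.3 points the same way. It opens "Any medical condition already present at screening or baseline should not be reported as an AE unless" and gives as the exception that the condition "worsens in severity or seriousness at any time during the study". Stopping study drug is not an exception in either place. Section 11.1.1 does list "Discontinuation of IMP" as a trigger for reporting, but only for laboratory or diagnostic test abnormalities.

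SAP v1.3 section 3.2.1 limits the evaluation to treatment-emergent events, defined as "AEs that begin or worsen on or after the date of first dose of study drug administration in open-label extension (OLE) period" and up to 30 days after the last dose. Section 5.4.1 then plans a table of "TEAEs leading to withdrawal of IMP by SOC and PT" and a separate listing of "TEAEs resulting in withdrawal of study drug". Section 5.4.2 adds a table of treatment-emergent events of special interest that led to discontinuation.

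Protocol section 12.4 itself promises a tabulation of adverse events leading to withdrawal of study drug, without confining it to treatment-emergent ones. SAP v1.3 section 5.2.3 separately summarises withdrawals from study drug by reason.

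**The concern.** The primary objective is long-term safety and tolerability (protocol 5.1.1), and stopping drug because of an adverse event is a direct measure of tolerability. Take a patient who enters the OLE with ongoing moderate muscle pain, tolerated to the end of the parent study, and later gives up bempedoic acid because of it, with the severity grade unchanged. That is an OLE withdrawal due to an adverse event. As written, the outputs designed to show such withdrawals would not contain it. The count of adverse-event withdrawals could then be too low. It could also differ from the count under the same reason in disposition, and no reconciliation is planned.

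**Working it through.** The plan gives no figure to reproduce. The check follows one patient through the planned outputs. The event is a clinical symptom, not a laboratory finding. It is not serious, began in the parent study, is unchanged in severity, and leads to withdrawal of study drug in the OLE.

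**Step 1, recording.** Protocol 12.4 keeps the event in the parent study. Section 11.1.3 does not reopen it, because neither severity nor seriousness has worsened. The trigger in 11.1.1 does not apply, because this is not a laboratory or diagnostic finding.

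**Step 2, classification.** The event neither begins nor worsens on or after the first OLE dose, so under SAP v1.3 section 3.2.1 it is not treatment-emergent.

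**Step 3, outputs in SAP v1.3.**

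| Output | Section | Is the event or patient there? |
|---|---|---|
| Treatment-emergent overview, SOC/PT and related-event tables | 5.4.1 | Event absent |
| Table of withdrawals due to adverse events | 5.4.1 | Absent |
| Listing of withdrawals due to adverse events | 5.4.1 | Absent |
| Events of special interest leading to discontinuation | 5.4.2 | Absent, even for myalgia or pain in extremity, which are Appendix 2 terms |
| Comprehensive listing of all adverse events, non-emergent ones flagged | 5.4.1 | Not settled: present only if the event is in the OLE data, and protocol 12.4 suggests it is not |
| Withdrawals from study drug by reason | 5.2.3 | Patient present, without term, severity or relatedness |
| Length of exposure | 5.2.8 | Patient present, with shortened exposure |

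**Step 4, scale.** The only input from the documents is the planned enrolment of about 1300 (protocol 6.5). The effect of k omitted patients on the withdrawal percentage is 100 × k / 1300:

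- k = 1: 100 × 1 / 1300 = 0.08 percentage points
- k = 5: 100 × 5 / 1300 = 0.38 percentage points
- k = 13: 100 × 13 / 1300 = 1.0 percentage point

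The values of k are illustrations. The documents give neither the number of patients entering with an ongoing event nor the number who later stop because of one.

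**Step 5, seriousness.** Sections 11.1.3 and 12.4 of the protocol use different tests. The first names severity or seriousness, the second severity alone, and section 11.1.4 notes that the two are not the same. SAP v1.3 section 3.2.1 uses worsening without defining it. Whether a carried-over event that becomes serious at unchanged severity enters the treatment-emergent SAE tables is therefore left open.

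**The case against.** The best defence is that the patient is not lost. Unacceptable AE is a listed reason for withdrawal (protocol 9.3.1). Reason and last-dose date go on the OLE eCRF (9.3.2), and SAP v1.3 section 5.2.3 tabulates reasons whatever the treatment-emergent status. This stands. A reader might infer that the patient vanishes from every OLE tolerability output, and that is not so. Disposition does not, however, say which event it was, how severe, or whether related.

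The case is also narrow. Laboratory abnormalities that lead to discontinuation become reportable under 11.1.1, and the laboratory tables work from measured values (SAP v1.3 section 5.4.4). Entry requires that the patient tolerated study drug to the end of the parent study (protocol 6.7), and an event that becomes incapacitating would be regraded and so count as worsened. All of this limits the frequency. None of it closes the gap, because the entry criteria do not exclude patients with ongoing adverse events.

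A reader might also infer that a carried-over event turning serious disappears. The documents do not support that: 11.1.3 makes it reportable, 11.2.2 requires it on the eCRF, and the SAP v1.3 listing of serious events is not confined to treatment-emergent ones. What remains is the mismatch in Step 5.

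Finally, the SAP does not repeat the carry-over sentence and takes precedence over the protocol on analysis (SAP v1.3 section 2). The eCRF instructions, which might soften the rule in practice, are not in the documents. That leaves the comprehensive listing uncertain. It does not rescue the withdrawal table and listing, which the SAP's own wording restricts.

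**Conclusion.** The gap is real but limited. Followed as written, the plan omits from the withdrawal table, the withdrawal listing and the special-interest discontinuation table any OLE withdrawal caused by a non-serious, non-laboratory event carried over at unchanged severity. The adverse-event withdrawal rate can be understated by about 0.08 percentage points per patient at about 1300 patients, and can disagree with disposition. This assumes that sites apply 12.4 and 11.1.3 literally. The number of such patients is unknown and probably held down by the entry criterion.

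Two stronger readings should be resisted. One is a definite count of missed withdrawals, which the documents cannot supply. The other is that the longest-exposed group would look best tolerated. Carried-over events from the parent treatment period did begin on drug in the former bempedoic acid group. But the rule applies equally to former placebo patients, and nothing in the documents shows more carried-over events, or more later withdrawals, in either group.

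SAP versions 1.0 to 1.2 had a withdrawal listing covering all adverse events. Those versions are superseded and the difference is not in itself an error, but it shows that the wider listing has already been specified once.

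**What to change.** - Leave the treatment-emergent definition as it is. Relabelling an event that neither began nor worsened in the OLE would contradict protocol 11.1.7 and SAP v1.3 section 3.2.1.
- In protocol 12.4 and 11.1.3, require that a carried-over event leading to withdrawal of study drug in the OLE be recorded in the OLE and linked to the parent-study event.
- In SAP v1.3 sections 5.4.1 and 5.4.2, base the withdrawal table, the withdrawal listing and the special-interest discontinuation table on any adverse event whose action taken in the OLE was withdrawal of study drug, whatever its onset. Flag events that are not treatment-emergent.
- Reconcile these counts with the disposition summary in 5.2.3.
- In protocol 12.4, extend the carry-over test from severity to severity or seriousness, so that it agrees with 11.1.3.

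The cost is a wording change in both documents and one instruction to sites for the adverse-event page. Action taken is already recorded for each adverse event (protocol 11.1.3). The downside is small: the adverse-event withdrawal count becomes slightly less favourable.

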12.5. Secondary Efficacy Endpoints

The secondary efficacy endpoints will be summarized descriptively using FAS. The change or percent change in lipid parameters will be calculated at each scheduled visit from the baseline of the parent study. No imputation is planned for missing data. Ninety-five percent (95%) CI will be provided for the estimates at each scheduled visit during the treatment period..

12.6. Other Safety Endpoints

Laboratory Results

Actual value or change from baseline (where appropriate) in clinical safety laboratories, including hematology, blood chemistry, HbA_{1C}, glucose, and urinalysis will be summarized at each scheduled visit.

Shift tables for selected safety laboratory parameters will be provided.

Physical Measurements

Height and weight will be summarized at each scheduled visit.

Vital Signs

Hear rate, SBP and DBP will be summarized at each scheduled visit.

Hepatic Safety

Actual value and change from baseline in liver-associated enzymes and TB will be summarized at each visit. In addition, the number and percent of patients with normal vs. abnormal values for ALT, AST, and TB will be summarized by their baseline and postbaseline status. Hy's law criteria (>3 × ULN for either ALT or AST, with accompanying TB >2 × ULN or patient's baseline) will also be applied to the data; any potential Hy's law cases will be listed separately. In the case of patients with Gilbert's disease, TB will be fractionated and the determination of $2 \times ULN$ based upon direct (conjugated) bilirubin. For patients with Gilbert's Disease $2 \times$ the conjugated bilirubin will be used as the criterion.

Musculoskeletal Safety

Adverse events of muscle-related symptoms will be summarized. Creatine kinase levels will be summarized by the value and change from baseline in the value, by visit. In addition, the number and percent of patients with normal vs. abnormal CK values will be summarized by their baseline and post-baseline status.

Diabetes and Hyperglycemia

Cases of new onset of diabetes will be recorded as AEs and will be summarized using the appropriate SOC. These events will be summarized by severity and relationship to study drug. Glucose and HbA_{1C} will be monitored at baseline and at Weeks 12, 52 and 78, and be summarized by history of diabetes.

Renal Safety

Baseline eGFR will be summarized for actual value and for baseline eGFR categories. Shift tables of eGFR category from baseline over the study, will be provided. Shift tables of urine protein (negative/positive) from baseline over the study, will be provided. Values of CK will be summarized by baseline eGFR category.

Neurocognitive Events

Neurocognitive events will be identified and evaluated by routine safety monitoring of PE findings and AEs. Summarization of neurocognitive events will occur using prespecified MedDRA terms and will be performed by SOC and PT, severity, and relationship to study drug.

Clinical Endpoints

Clinical endpoints using standardized definitions will be adjudicated by an independent blinded expert CEC for all ongoing Phase 3 studies in the bempedoic acid program. Investigator-reported clinical endpoints and adjudicated clinical endpoints will be summarized by event type. Additional details regarding the clinical endpoints and their definitions will be included in CEC Charter.

13. DIRECT ACCESS TO SOURCE DATA/DOCUMENTS

13.1. Study Monitoring

The Sponsor (or its authorized representative) has the obligation to follow this study closely to ensure that the study is conducted in accordance with the protocol, International Conference on Harmonisation (ICH) and GCP guidelines, national and international regulatory requirements, and the current Declaration of Helsinki throughout its duration by means of personal visits to the Investigator's facilities and other communications.

These visits will be conducted to evaluate the progress of the study, verify the rights and well-being of the patients are protected, and verify the reported clinical study data are accurate, complete, and verifiable from source documents. This includes review of ICDs, results of tests performed as a requirement for participation in this study, and any other medical records (eg, laboratory reports, clinic notes, study drug dispensing log, pharmacy records, patient sign-in sheets, patient-completed questionnaires, telephone logs, ECGs) required to confirm information contained in the eCRFs.

The monitoring strategy for the study foresees a risk-based monitoring approach, in line with the relevant Food and Drug Administration (FDA) and European Medicines Agency (EMA) recommendations, and will be described in details by the study-specific risk-based-monitoring plan.

A monitoring visit should include a review of the essential clinical study documents (regulatory documents, case report forms, medical records and source documents, drug disposition records, patient informed consent forms, etc) as well as discussion on the conduct of the study with the Investigator and staff.

The monitor should conduct these visits as frequently as appropriate for the clinical study. The Investigator and staff should be available during these visits for discussion of the conduct of the study as well as to facilitate the review of the clinical study records and resolve/document any discrepancies found during the visit.

All monitoring activities will be reported and archived. In addition, monitoring visits will be documented at the clinical site by signature and date on the study-specific monitoring log.

13.2. Audits and Inspections

Representatives of the Sponsor or its authorized clinical quality assurance group may visit a clinical site at any time during the study to conduct an audit of the study in compliance with regulatory guidelines and company policy. These audits will require access to all study records, including source documents, for inspection and comparison with the eCRFs. Patient privacy must be respected. The Investigator and clinical site personnel are responsible for being present and available for consultation during routinely scheduled site audit visits conducted by the Sponsor or its authorized representative.

The clinical study may also be inspected by the FDA or EMA (or other regulatory authority) to verify that the study was conducted in accordance with protocol requirements, as well as the applicable regulations and guidelines.

In the event the Investigator is contacted by regulatory authorities who wish to conduct an inspection of the clinical site, the Investigator will promptly notify the Sponsor of all such requests and will promptly forward a copy of all such inspection reports.

